#### 5.3.1 Primary Independent Variable(s) – Exposure Groups

- Group 1: Metal-on-Metal total hip arthroplasty
  - o ICD-9: 00.75, hip bearing surface, metal-on-metal
  - o ICD-10 Codes:
    - OSRR01Z, Replacement of Right Hip Joint, Femoral Surface with Metal Synthetic Substitute, Open Approach
    - OSRS01Z, Replacement of Left Hip Joint, Femoral Surface with Metal Synthetic Substitute, Open Approach
    - OSRS019, Replacement of Left Hip Joint, Femoral Surface with Metal Synthetic Substitute, Cemented, Open Approach
    - OSRS01A, Replacement of Left Hip Joint, Femoral Surface with Metal Synthetic Substitute, Uncemented, Open Approach
- Group 2: Non-Metal-on-Metal total hip arthroplasty
  - o ICD-9 Codes
    - 00.74, hip bearing surface, metal-on-polyethylene (MoP)
    - 00.76, hip bearing surface, ceramic-on-ceramic (CoC)
    - 00.77, hip bearing surface, ceramic-on-polyethylene (CoP)
  - o ICD-10 Codes:
    - OSRR03Z, Replacement of Right Hip Joint, Femoral Surface with Ceramic Synthetic Substitute, Open Approach
    - OSRS03Z, Replacement of Left Hip Joint, Femoral Surface with Ceramic Synthetic Substitute, Open Approach
    - OSRS039, Replacement of Left Hip Joint, Femoral Surface with Ceramic Synthetic Substitute, Cemented, Open Approach
    - OSRS03A, Replacement of Left Hip Joint, Femoral Surface with Ceramic Synthetic Substitute, Uncemented, Open Approach
- Age and gender-similar OA patients

Introduced in October 2005, ICD-9 bearing surface code identifiers (00.74 for Metal on p, 00.75 for M-M, 00.76 for C-C, 00.77 C-PE) are optional modifiers that can be reported in conjunction with the primary procedure code for total hip arthroplasty. A limitation on this data is that it has been shown to have both under-coding and misclassification when coded.

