#### 5.4.3 Risk of Heart Failure Associated with MoM Implants

Cox proportional hazards regression will be performed to determine HRs of heart failure with 95% Cis in MoM implants versus non-MOM implant and MoM implants versus RA patients without arthroplasty. Propensity score matching or stratification will be used to control for confounding.

If a significantly higher risk of heart failure is identified for patients with MoM implants, Cox proportional hazards regression will be conducted to determine risk factors for a diagnosis of heart failure.

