#### 5.4.4 Sensitivity Analyses

- Limit outcome to hospitalization for heart failure
- Stratification by ICD-9 and ICD-10 codes (ICD-10 codes may be improved for ascertaining both MoM prostheses use and for heart failure as compare to ICD-9 codes)
- Stratification for non-MoM comparison (exclude MoP from the comparator group)

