## 5.6 Limitations of the Research Methods

As with any database study, identification of medical events, such as heart failure or co-morbidities, is limited to data that are captured as part of the medical record or claims, which are not primarily collected for research purposes, and will rely on appropriate diagnostic codes to detect these events. Misclassification bias can result if study patients are not categorized correctly with regards to exposure or outcome. Limited patient follow-up time will hinder our ability to study the long-term risk of heart failure. The study results will be generalizable to patients meeting the inclusion and exclusion criteria.

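### MoM exposure rests on ICD-9 bearing codes that the protocol itself calls misclassified, and no planned analysis quantifies what that error does to the hazard ratios

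*Protocol*

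**What the plan says.** - **Exposure (Protocol 5.3.1).** Under ICD-9, MoM is defined by a single code, "ICD-9: 00.75, hip bearing surface, metal-on-metal". Non-MoM is defined by 00.74, 00.76 or 00.77. The section adds that these codes "are optional modifiers that can be reported in conjunction with the primary procedure code for total hip arthroplasty", and then: "A limitation on this data is that it has been shown to have both under-coding and misclassification when coded". It gives no sensitivity, specificity or predictive value.
- **Primary analysis (5.4.3).** "Cox proportional hazards regression will be performed to determine HRs of heart failure with 95% Cis in MoM implants versus non-MOM implant", and likewise against patients without arthroplasty. (That sentence names RA for the second comparator. Sections 4.2.1 and 5.4 name OA, which is used here.) The only bias control is for confounding: "Propensity score matching or stratification will be used to control for confounding".
- **Sensitivity analyses (5.4.4).** There are three: "Limit outcome to hospitalization for heart failure"; a split by ICD-9 and ICD-10, on the ground that ICD-10 may ascertain MoM use better; and removal of MoP from the comparator.
- **Limitations (5.6).** "Misclassification bias can result if study patients are not categorized correctly with regards to exposure or outcome". No direction or size is given.

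**The concern.** The protocol concedes error in the variable that defines its main contrast, then reports hazard ratios and ordinary 95% intervals as if that variable were exact. MoM may be a minority bearing; it was about 10% of hips in the registry linkage study cited in section 3. A small false-positive rate among many non-MoM hips can then make up a large part of the coded MoM group.

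None of the three sensitivity analyses measures this:
- Restricting the outcome leaves exposure untouched.
- Dropping MoP narrows the comparator but leaves false positives in the MoM group.
- The code-version split leaves the ICD-9 stratum with all its error and gives no corrected estimate. Nor is the ICD-10 stratum a clean reference: the listed MoM codes describe the femoral surface only (for example "Replacement of Right Hip Joint, Femoral Surface with Metal Synthetic Substitute, Open Approach"), which does not establish a metal-on-metal pair.

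The research question is whether MoM patients are at increased risk. A modest true effect, in either direction, could be reported as near-null, with an interval that reflects sampling error alone. Section 5.4.3 also makes the risk-factor model conditional on a significantly higher MoM risk, so attenuation can affect whether that model is run.

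**Working it through.** **The plan's own figures.** The protocol states no target hazard ratio, power or event number; 18,521 MoM patients (5.3.4) is a count. As a check on the cited same-database study, its odds ratios recompute to 0.930 (0.870 to 0.995) at three years and 0.912 (0.860 to 0.968) at four. These agree with the printed 0.93 and 0.91.

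**Inputs from the protocol.**
- MoM share in the registry linkage study: 53,529/(53,529 + 482,247) = 0.0999.
- MoM patients: 18,521.
- Heart failure in MoM patients at three years: 6.60%.

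**Assumptions.** Sensitivity (Se), specificity (Sp), a second MoM share of 30%, five years of follow-up, 1:1 comparison, and error unrelated to heart failure.

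**Formulas, MoM vs non-MoM.** With p the true MoM share among coded hips:
- PPV = p·Se / [p·Se + (1−p)(1−Sp)]
- q (true MoM among coded non-MoM) = p(1−Se) / [p(1−Se) + (1−p)Sp]
- HR seen ≈ [1 + PPV(HR−1)] / [1 + q(HR−1)]

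Example, p = 0.10, Se/Sp 0.80/0.90: PPV = 0.08/(0.08 + 0.09) = 0.471; q = 0.02/(0.02 + 0.81) = 0.024. A true 1.20 gives 1.0941/1.0048 = 1.089.

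**Precision.** Rate = −ln(1 − 0.066)/3 = 0.02276 per year. Events = 18,521 × 0.02276 × 5 ≈ 2,108 in the MoM group. At 1:1 the 95% factor is exp(1.96·√(2/2,108)) = 1.062.

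| p | Se/Sp | PPV | True 1.20 seen as (95% CI) | True 1.10 | True 0.90 |
|---|---|---|---|---|---|
| 10% | 0.95/0.98 | 84% | 1.17 (1.10–1.24) | 1.08 | 0.92 |
| 10% | 0.90/0.95 | 67% | 1.13 (1.06–1.20) | 1.07 | 0.93 |
| 10% | 0.80/0.90 | 47% | 1.09 (1.03–1.16) | 1.045 (0.98–1.11) | 0.96 |
| 30% | 0.95/0.98 | 95% | 1.19 (1.12–1.26) | 1.09 | 0.91 |
| 30% | 0.90/0.95 | 88% | 1.17 (1.10–1.24) | 1.08 | 0.92 |
| 30% | 0.80/0.90 | 77% | 1.14 (1.07–1.21) | 1.07 | 0.93 |

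At 1:1 only the third row's interval excludes a true 1.20. In the second row the unrounded upper limit is 1.201.

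**Independent check.** This took PPV 0.80 and q 0.05 directly, with 18,521 per group and 7.06% comparator risk (the cited three-year MoP figure). A true 1.5 is seen as 1.37 by formula and 1.35 in simulated Cox fits; a true 1.2 as 1.15 and 1.13. Power for a true 1.1 falls from 70% to 47%; for a true 1.2 it stays near 96%.

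**MoM vs OA.** The OA group is not defined by the bearing code, and false MoM patients are non-MoM hips. So HR seen ≈ PPV·HR + (1−PPV)·g, with g the non-MoM vs OA hazard ratio (assumed). At PPV 0.80 a true 1.20 becomes:
- 0.96 + 0.16 = 1.12 if g = 0.8
- 0.96 + 0.20 = 1.16 if g = 1.0
- 0.96 + 0.26 = 1.22 if g = 1.3, away from 1

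At PPV 0.70 and g = 0.7 a true 1.10 becomes 0.77 + 0.21 = 0.98, which crosses 1.

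**The case against.** **The protocol is not silent.** It discloses exposure misclassification twice and plans a code-version split aimed partly at exposure. That stands as disclosure. As a remedy it is weak, for the reasons given above.

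**A bias analysis may sit in an SAP not shown.** This is fair, and its absence alone would be no finding. But section 5.4.4 already fixes a list of sensitivity analyses, one of them aimed at exposure coding, and that list leaves the stated defect unquantified.

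**The size is assumed.** This stands. No code accuracy is given, and the 10% share comes from a registry linkage study, not from Medicare. Bearing codes are optional, so the share that matters is MoM among coded hips, which is unknown. Under-coding as such drops uncoded hips from both arthroplasty groups; it does not in itself shrink the hazard ratio.

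**The harm is limited.** For a true 1.20, every interval in the table still excludes 1, so a raised risk would still be reported, though understated. A reader might infer that the study would give false reassurance, or that its interval would miss the truth. The figures support the first only for smaller effects, such as a true 1.10 in the worst setting, and the second, for a true 1.20 at 1:1, only in that same setting.

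**The bias is not one-sided.** This also stands. The registry linkage study and the same-database study cited in section 3 reported lower MoM risk (0.90; 0.93 and 0.91), and a protective effect is attenuated too. Correction could strengthen reassurance as well as weaken it.

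**Conclusion.** The concern holds for MoM vs non-MoM. With error unrelated to heart failure, that hazard ratio is pulled toward 1 and its interval leaves out an error the protocol concedes. Over the assumed range, a true 1.20 is seen as anything from 1.19 down to 1.09, and a true 0.90 as 0.91 to 0.96. The documents do not say whether miscoding is related to heart failure risk; if it is, attenuation is not assured.

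A reader might infer that both co-primary hazard ratios shrink toward 1. The documents do not support this. MoM vs OA moves toward the non-MoM vs OA value, which may lie on either side of 1, so only the presence of bias follows and not its direction.

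This is a gap worth closing cheaply before analysis. It does not show that the study must miss a real risk.

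**What to change.** Add two items to Protocol section 5.4.4, for the ICD-9-coded exposure.

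1. A prespecified quantitative bias analysis of the MoM vs non-MoM and MoM vs OA hazard ratios over a stated sensitivity/specificity grid (for example 0.80–0.98 and 0.90–0.99). Report corrected hazard ratios with intervals that include this uncertainty. Use the MoM share among coded hips in the study data, not an outside figure. That observed share also limits the grid, since it equals p·Se + (1−p)(1−Sp): a true 10% share at 0.80/0.90 implies 0.08 + 0.09 = 17% coded MoM. For MoM vs OA, fit coded non-MoM against OA as well, to inform g.
2. A repeat of the MoM vs non-MoM Cox model that excludes index claims carrying more than one bearing code.

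State in section 5.4.3 that a null or near-null MoM vs non-MoM result will be interpreted together with item 1. Restricting to hospitals that code bearings most completely is not needed: it addresses under-coding, and a hospital that always codes can still code wrongly.

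The cost is protocol wording and some programming on data already held. The downside is a wider corrected interval that depends on the assumed accuracy range.

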#### 5.3.2 Subgroup/Stratification Variable(s)

• N/A

#### 5.3.2.1 Patient Demographics

- Age at index
- Gender
- Race
- Calendar year
- Geographic region
- Insurance type
- BMI

#### 5.3.2.2 Procedural Characteristics

- Year of index date
- Hospital length of stay (days)
- Medicare Severity Diagnosis Related Groups (MS-DRG) (Major Complication/Comorbidity, Complication/Comorbidity, No Complication/Comorbidity)

#### 5.3.2.3 Patient Clinical Characteristics

- Deyo-Charlson Comorbidity Index (CCI): the CCI is an aggregate measure of comorbidity created by using select diagnoses associated with chronic disease (e.g., heart disease, cancer). Higher scores are indicative of greater comorbid burden. The CCI includes 19 medical conditions and weights these conditions from +1 to +6.
- Elixhauser comorbidity system: the Elixhauser comorbidity system is a set of 30 comorbidity indicators that is used for adjustment of comorbidity in observational studies. Van Walraven and colleagues developed a summary score for the Elixhauser comorbidities by modeling in-hospital mortality with inpatient admission data. The summary score is a weighted combination of the 30 Elixhauser comorbidities, where a larger comorbidity weight indicates a stronger association between the comorbidity and in-hospital mortality.
- Medicare Enrollment State Buy-In Status (Yes/No)
- Individual Elixhauser and Charlson comorbidity categories:
  - Specific CV comorbidities: dyslipidemia, hypertension, diabetes, peripheral vascular disease, TIA and obesity
- Other comorbidities that have been associated with increased mortality such as: chronic obstructive pulmonary disease, obstructive sleep apnea, cardiac arrhythmias, HIV, and cancer
- Rheumatoid Arthritis, Psoriatic Arthritis, Osteoporosis and Osteopenia
- Dislocation and instability post index
- Metalosis post index

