# 1. Protocol Synopsis

Title	Incidence and risk of heart failure in patients following metal-on-metal (MoM) hip arthroplasty	
Study Objectives	Co-Primary: To estimate the incidence and evaluate the risk of heart failure among patients undergoing MoM arthroplasties of the hip compared with those with alternative types of arthroplasties (non-MoM)	
	Co-Primary: To estimate the incidence and evaluate the risk of heart failure among patients undergoing MoM arthroplasties of the hip compared with age and gender similar Osteoarthritis (OA) cohort without arthroplasty	
Data Sources	Medicare SAF	
Study Design	Retrospective Cohort Study	
Study Population	Patients are eligible if they are (1) ≥ 65 years, (2) undergo an elective, primary total hip arthroplasty (THA) performed in the inpatient setting between October 1, 2005, and December 31, 2017 (index procedure), and (3) enrolled in the data source for at least 365 days prior to index procedure (baseline period). Patient exclusions include a diagnosis of heart failure, THA/TKA arthroplasty, or metal implants during the baseline period or concurrent diagnosis of hip fracture during the index THA procedure.	
Endpoints	2 recorded Heart Failure-related diagnosis codes	
Data Analyses	Descriptive statistics on baseline characteristics with comparison between exposure groups; Unadjusted incidence rate for heart failure; Propensity scores; Cox Regression to determine HRs with 95% Cl	

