#### 4.2.2 Secondary objective(s):

• To describe and compare the baseline characteristics of the exposure groups and to identify important prognostic variables that should be balanced between the exposure groups and which should be included in the propensity score of the primary analysis.

[figure not shown]

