#### 5.3.3.3 Outcomes for Secondary Objective(s)

• Variables noted in sections above

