## 5.4 Data Analysis(es)

The goals of these analyses are to: 1) determine the characteristics of patients implanted with MoM and non-MOM hip implants and OA patients with arthroplasty, and 2) evaluate the risk of heart failure among patients with MoM implants compared to non-MOM implants or OA without arthroplasty.

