#### 5.4.1 Descriptive Statistics

Descriptive statistics will be calculated for both study cohorts. Categorical variables will be summarized by frequencies and proportions, and continuous variables will be summarized by means and standard deviations or medians and interquartile ranges. Differences between study cohorts will be assessed using Chi-square tests for categorical data and t-tests or Wilcoxon rank-sum tests for continuous data, as indicated.

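### Two post-index events are listed as patient characteristics, so by default they get percentages that ignore follow-up and become propensity score candidates

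*Protocol*

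**What the plan says.** Section 5.3.2.3 (Patient Clinical Characteristics) ends its list of comorbidity indices and conditions with "Dislocation and instability post index" and "Metalosis post index". Neither appears in the endpoint sections 5.3.3.1 and 5.3.3.2.

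Section 5.3.3.3 defines the variables for the secondary objective as "Variables noted in sections above", with no exception. The objective itself (4.2.2) is "To describe and compare the baseline characteristics of the exposure groups", and it goes on to identify the prognostic variables that belong in the propensity score.

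The synopsis plans "Descriptive statistics on baseline characteristics with comparison between exposure groups". The first goal in 5.4 is to "determine the characteristics of patients implanted with MoM and non-MOM hip implants". The method in 5.4.1 is frequencies and proportions for categorical variables, and "Differences between study cohorts will be assessed using Chi-square tests for categorical data". Person-time is defined in 5.4.2 for heart failure only. The Cox models in 5.4.3 are also for heart failure. A second one, on risk factors, is run only if MoM patients show a significantly higher risk.

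**The concern.** A variable labelled as occurring after the index date cannot be a baseline characteristic, yet the protocol routes these two into an objective about baseline characteristics. Two consequences need checking.

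First, the only stated way to describe and compare listed variables is a percentage with a chi-square test. The two items have no time window, and 5.2.1 requires no minimum follow-up. The percentage is therefore not a risk over any defined period. If one arthroplasty cohort is followed longer on average, its percentage rises for that reason alone, or a real difference in rates is hidden.

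Second, the same routing offers both events to the propensity score selection. They happen after the implant is chosen and may be consequences of it. Metallosis could also lie on a path from the bearing to heart failure. A score that contained them would adjust for something downstream of exposure, and this route could reach the primary hazard ratio.

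**Working it through.** The protocol states no rate, power or follow-up figure for these two events, so there is no figure to reproduce.

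**1. Which analyses reach the two items.**
- 5.4.1 (proportions, chi-square) reaches them by default, because they are listed variables and no other descriptive method is given. It does not name them.
- 5.4.2 (person-time) does not, because it is stated for heart failure.
- The conditional risk-factor model in 5.4.3 could use them as predictors, but would not report how often they occur in each cohort.
- 4.2.2 together with 5.3.3.3 makes them propensity score candidates, since nothing excludes them.

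**2. Possible follow-up.** The inputs are the index window (1 October 2005 to 31 December 2017) and the study end (30 June 2018), both from 5.2.
- Longest: 1 October 2005 to 30 June 2018 = 12.74 years.
- Shortest: 31 December 2017 to 30 June 2018 = 0.50 year.
- Mean if index dates are evenly spread (assumption), before any other stopping event: (12.74 + 0.50)/2 = 6.62 years.

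**3. Ratio of raw percentages when the true rates are equal.** Assumptions: constant hazard, the same rate in both cohorts, and the mean follow-up shown. Percentage = 1 − exp(−rate × mean years).

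| Mean follow-up (years) | 2 per 1,000 | 5 per 1,000 | 10 per 1,000 |
|---|---|---|---|
| equal | 1.000 | 1.000 | 1.000 |
| 3.5 vs 3 | 1.166 | 1.165 | 1.164 |
| 4 vs 3 | 1.332 | 1.330 | 1.327 |
| 5.5 vs 5 | 1.099 | 1.099 | 1.097 |
| 6 vs 5 | 1.199 | 1.197 | 1.194 |
| 7.12 vs 6.62 | 1.075 | 1.074 | 1.073 |
| 7.62 vs 6.62 | 1.150 | 1.148 | 1.145 |

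The ratio of percentages is close to the ratio of mean follow-up. Example at 5 per 1,000, 6 vs 5 years: 1 − exp(−0.030) = 2.96% and 1 − exp(−0.025) = 2.47%.

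**4. Masking.** 1 − exp(−0.005 × 6) = 1 − exp(−0.006 × 5) = 2.96%. The percentages agree although the rate ratio is 0.006/0.005 = 1.20.

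**5. Chi-square behaviour.** Take 18,521 per cohort. This is the MoM count from the previous analysis cited in 5.3.4, and the equal-sized comparator is assumed. With 5 vs 4.5 years of mean follow-up and equal rates, a two-sided 5% test rejects with probability 0.165, 0.34, 0.59 and 0.86 at 2, 5, 10 and 20 per 1,000 person-years. With equal follow-up it rejects at 0.05.

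**6. Propensity score route.** This cannot be sized from the document. It rests on the wording alone.

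**The case against.** The strongest reply is that the criticised analysis is inferred. No sentence says that dislocation or metallosis will be tested by chi-square. The synopsis and 4.2.2 both speak of baseline characteristics, which these items are not, by their own label. Whether an ancillary event is shown as a percentage or a rate is also detail that a SAP may settle. This stands in part: chi-square applies only by default. What remains is in the protocol itself. It places post-index events in the characteristics list and passes that list on without exception.

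A second reply is that the sizes are all assumed. That is correct. Nothing in the document shows that follow-up differs between the MoM and non-MoM cohorts.

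A third is that "Year of index date" is a listed variable and that matching or stratification is planned. If year enters the score, matched cohorts would have similar administrative follow-up. That also stands, but 5.4.1 does not say whether its tables use matched cohorts. Showing index year beside unmatched percentages reveals a difference without correcting for it.

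Finally, no endpoint depends on these two percentages. This is true, and it is why the point is minor.

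**Conclusion.** The point holds as a classification error with two avoidable consequences: a default summary that ignores follow-up, and propensity score eligibility for events that occur after exposure. Under the assumed rates, a half-year gap in mean follow-up would move the ratio of percentages to between 1.07 and 1.17, and a one-year gap to between 1.15 and 1.33. With no gap there is no distortion. The figures assume a constant hazard. If events cluster soon after surgery, the ratios would be nearer to 1.

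Three stronger readings are tempting, and the document does not support them:
- A reader might infer that the 0.5 to 12.7 year range is itself a bias. It is not. Only a difference between cohorts matters, and that is not given.
- A reader might infer that the chi-square comparison threatens the heart failure results. It does not touch them.
- A reader might infer that the two events will be in the propensity score and that the primary hazard ratio is therefore biased. The protocol leaves them eligible but does not say that they will be selected, and 4.2.2 speaks of baseline characteristics.

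This is an optional improvement, worth making because it is cheap.

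**What to change.** Move both items out of 5.3.2.3 into a short list of descriptive post-index events, so that they also leave the 5.4.1 chi-square comparison. State that they are not eligible for the propensity score.

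Report each one in the MoM and non-MoM cohorts only, as events per 1,000 person-years with 95% CI. Person-time runs from the index date to the first such event or the end of follow-up under 5.2. The 30-day delay in 5.4.2 serves the heart failure endpoint and is not needed here. Because revision ends follow-up, state that an event coded on the revision date is counted.

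The cost is a wording change and two extra outputs, which should be labelled descriptive. The heart failure endpoints and models need no change.
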